4.4 Coenrollment Guidelines

Sites are encouraged to coenroll participants in A5243, "Plan for Obtaining Human Biological Samples at Non-U.S. Clinical Research Sites for Currently Unspecified Genetic Analyses". Coenrollment in A5243 does not require permission from the A5338 protocol chairs.

For specific questions and approval for coenrollment in other studies, sites should first check the PSWP or contact the protocol team via e-mail as described in the Study Management section.

5.0 STUDY TREATMENT

Study treatment is defined as a single dose of depot medroxyprogesterone acetate (DMPA). ARV and TB therapy are required; however they will NOT be supplied through the study.

5.1 Regimen, Administration, and Duration

5.1.1 Regimen

At study entry/week 0, participants will receive:

Depot medroxyprogesterone acetate (DMPA) 150 mg administered intramuscularly (IM) as a single-dose.

NOTE: An optional additional dose of DMPA will be provided at no cost to all study participants who successfully complete all 12 weeks of the study, experience no AEs from the first injection, are interested in continuing with DMPA outside of the protocol, and after confirmation of a negative pregnancy test.

Required ARV therapy (not provided through study):

- Efavirenz (EFV) 600 mg orally once daily in combination with 2 or more NRTIs.
- Two or more NRTIs

NOTES:

- a. Acceptable NRTIs include the following:
 - zidovudine (ZDV)
 - lamivudine (3TC)
 - emtricitabine (FTC)
 - didanosine (ddI)
 - stavudine (d4T)
 - abacavir (ABC)
 - tenofovir disoproxil fumarate (TDF)
 - b. Refer to section 5.4.2 for the prohibited NRTI combinations.
- Women who are not already receiving HIV treatment at the time of screening may initiate cART at any time between 2 and 8 weeks after starting TB treatment, at the discretion of the treating physician and health care provider at the local clinic.
 - ARV therapy will not be provided through the study. For participants requiring changes in ARV therapy during the study, see sections 6.2.4 and 8.2 for follow-up and study discontinuation.

Required TB treatment (not provided through study):

- Rifampicin (RIF) 600 mg orally once daily.

- Isoniazid (INH) 300 mg orally once daily.

NOTE: Pyridoxine (vitamin B₆), if recommended by local standard of care with INH, will not be supplied through the study and must be obtained locally by the site.

- Participants must be on the continuation phase of TB treatment with a minimum of 12 weeks of TB treatment remaining.

5.1.2 Administration

The 1 mL vial or the 1 mL pre-filled syringe of DMPA should be vigorously shaken just before use to ensure that the dose being administered represents a uniform suspension. A total of 1 mL (150 mg) of DMPA should be injected deeply into the gluteal or deltoid muscle.

5.2 Study Product Formulation and Preparation

Depot medroxyprogesterone acetate (DMPA) is supplied in vials and pre-filled syringes, each containing 1 mL of medroxyprogesterone acetate sterile aqueous suspension at a concentration of 150 mg/mL. The product must be stored at 20°C to 25°C (68°F to 77°F).

5.3 Pharmacy: Product Supply, Distribution, and Accountability

5.3.1 Study Product Acquisition/Distribution

Depot medroxyprogesterone acetate (DMPA) will be supplied by Greenstone LLC.

Study product will be available through the National Institute of Allergy and Infectious Diseases (NIAID) Clinical Research Products Management Center (CRPMC). The site pharmacist should obtain the study product(s) for this protocol by following the instructions in the manual *Pharmacy Guidelines and Instructions for DAIDS Clinical Trials Networks* in the section Study Product Management Responsibilities.

Any study product not provided by the study must comply with the NIAID (DAIDS) policy that outlines the process for authorizing the use of study products not marketed in the US in NIAID (DAIDS)-supported and/or -sponsored clinical trials. This policy is available on the NIAID (DAIDS) website at: <http://www.niaid.nih.gov/LabsAndResources/resources/DAIDSClinRsrch/Documents/NonFDAApprovedProducts.pdf>

5.3.2 Study Product Accountability

The site pharmacist is required to maintain complete records of all study products received from the NIAID CRPMC and subsequently dispensed. All unused study products must be returned to the NIAID CRPMC (or as otherwise directed by the

sponsor) after the study is completed or terminated. The site pharmacist at non-US Clinical Research Sites (CRSs) must follow the instructions in the manual *Pharmacy Guidelines and Instructions for DAIDS Clinical Trials Networks* in the section Study Product Management Responsibilities.

5.4 Concomitant Medications

Whenever a concomitant medication or study agent is initiated or a dose changed, investigators must review the concomitant medication's and study agent's most recent package insert, Investigator's Brochure, or updated information from DAIDS to obtain the most current information on drug interactions, contraindications, and precautions.

Additional drug information may be found on the updated ACTG Drug Interactions Database located at: http://tdm.pharm.buffalo.edu/home/di_search/Search.

5.4.1 Required Medications

EFV-based cART, RIF, and INH (refer to section 5.1.1)

5.4.2 Prohibited Medications

- NRTIs are allowed, however, the following NRTI combinations are prohibited:
 - ZDV and d4T
 - 3TC and FTC
 - ABC and ddl
 - ABC and TDF
 - 3TC and d4T
 - ddl and d4T
- Other prohibited medications are listed on the A5338 PSWP.

5.4.3 Precautionary Medications

Precautionary medications are listed on the A5338 PSWP.

6.0 CLINICAL AND LABORATORY EVALUATIONS

6.1 Schedule of Events

Evaluation	Screening	Entry	On-Study (Weeks) and Visit Windows						Premature Study Discontinuation
		Week 0	2	4	6	8	10	12	
			±3 days	±3 days	±3 days	±3 days	±7 days	±7 days	
Documentation of HIV-1 and TB infection	X								
Medical History	X								
Menstrual Baseline and Interval History	X	X	X	X	X	X	X	X	
Medication History	X								
Clinical Assessments	X	X	X	X	X	X	X	X	X
Concomitant Medications		X	X	X	X	X	X	X	X
Adherence Assessments (cART and TB medications)	X	X	X	X	X	X	X	X	X
Hematology	X			X				X	X
Chemistry	X			X				X	X
Liver Function Tests	X			X				X	X
Pregnancy Test	X	X		X				X	X
Plasma Progesterone Levels			X	X	X	X	X	X	X
Serum FSH (see section 6.3.8)	X								
CD4+/CD8+		X							
HIV-1 RNA		X						X	
DMPA Injection		X						X	
DMPA PK		X	X	X	X	X	X	X	
Whole blood for Drug Metabolism Genotype		X							
Stored Serum for Bone Metabolism Biomarkers		X						X	

6.2 Timing of Evaluations

6.2.1 Screening Evaluations

Screening evaluations must occur prior to the participant's starting any study medications, treatments, or interventions. At the time of screening, participants must have completed the intensive phase and be in the continuation phase of TB treatment. Participants must require at least 12 more weeks of TB treatment at the time they receive the DMPA injection at study entry.

Site staff are encouraged to contact/liaise with primary care physicians at TB clinics for identification of eligible participants prior to completion of the intensive phase of TB treatment. Information about the location of the ARV clinic and planned timing of cART initiation should be obtained. The identified participants will be given appointments for the research clinic as soon as they are initiated on cART. Site staff will obtain contact details of these potential participants to remind them about scheduled screening appointments. Eligible participants will be enrolled as soon as eligibility is determined.

Screening evaluations to determine eligibility must be completed within 30 days prior to study entry unless otherwise specified. In addition to data being collected on participants who enroll into the study, demographic, clinical, and laboratory data on screening failures will be captured in a Screening Failure Results form and entered into the ACTG database.

6.2.2 Entry Evaluations

Entry evaluations must be completed on the day of registration after eligibility is determined from the screening evaluations. Participant must begin treatment the same day of registration. Entry evaluations must be completed prior to DMPA administration.

Enrollment and completion of entry evaluations after the start of the monthly menstrual flow is preferred.

6.2.3 Post-Entry Evaluations

Post-entry evaluations occur after study entry and injection of DMPA. Study visits are scheduled as indicated in the Schedule of Events (SOE) in section 6.1. The final visit is the week 12 visit.

The visit windows for post-entry evaluations are ± 3 days for weeks 2, 4, 6, and 8, and ± 7 days for weeks 10 and 12. The evaluations at weeks 10 and 12 should be performed as close as possible to the ideal visit date. If the week 10 or week 12 PK sampling is rescheduled, the reschedule date must be within the original visit window for the visit. There must be at least 3 days between the PK samples collected at each visit.

NOTE: All PK visits must be scheduled to occur following at least 2 consecutive doses of RIF and EFV in those participants who take TB medications <7 days a week.

Participants who elect to receive a second dose of DMPA at week 12 (see section 6.3.11) will have no further follow-up after the second dose of DMPA is administered.

Women who wish to continue receiving DMPA after completing the study will be referred to a family planning program or a program at their local clinic.

6.2.4 Discontinuation Evaluations

Evaluations for Registered Participants Who Do Not Start Study Treatment

All case report forms (CRFs) must be completed and keyed for the period up to and including week 0.

Premature Study Discontinuation

Participants who prematurely discontinue from the study will have the premature discontinuation evaluations performed as per section 6.1 and then be taken off study.

6.3 Instructions for Evaluations

All clinical and laboratory information required by this protocol is to be present in the source documents. Sites must refer to the Source Document Guidelines on the DAIDS Web site for information about what must be included in the source document: <http://www.niaid.nih.gov/labsandresources/resources/daidsclinrsrch/documents/sourcedocappndx.pdf>

All stated evaluations are to be recorded on the CRF and keyed into the database unless otherwise specified. This includes events that meet the International Conference on Harmonisation (ICH) definitions for a serious adverse event.

- Results in death
- Life-threatening
- Requires inpatient hospitalization or prolongation of existing hospitalization
- Results in persistent or significant disability/incapacity
- Congenital anomaly/birth defect
- Other important medical event (may not be immediately life-threatening or result in death or hospitalization but may jeopardize the patient or may require intervention to prevent one of the events listed above.

To grade diagnoses, signs and symptoms, and laboratory results, sites must refer to the DAIDS Table for Grading the Severity of Adult and Pediatric Adverse Events (DAIDS AE Grading Table), Version 1.0, December 2004 (Clarification, August 2009), which can be found on the DAIDS RSC Web site: <http://rsc.tech-res.com/safetyandpharmacovigilance/>.

6.3.1 Documentation of HIV-1 and TB Infection

HIV-1 Infection

Section 4.1.1 specifies assay requirements for HIV-1 documentation. HIV-1 documentation is not recorded on the CRF.

TB Infection

Section 4.1.2 specifies the clinical and laboratory requirements for confirmed or probable TB diagnosis. The TB diagnosis (ie, date of diagnosis and confirmed or probable) will be recorded on the CRF; however TB documentation will not be recorded.

6.3.2 Medical History

The medical history must include all diagnoses identified by the ACTG criteria for clinical events and other diagnoses. In addition to reporting in the CRF all diagnoses within the past 30 days, the following diagnoses should be reported regardless of when the diagnosis was made.

- AIDS-defining conditions
- Bone fractures (verbal history accepted)
- Coronary heart disease
- Cancer (exclusive of basal/squamous cell skin cancer)
- Tuberculosis
- Documentation of hepatitis B (surface antigen and core antibody) at any time prior to entry
- Documentation of hepatitis C (antibody) at any time prior to entry

Any allergies to any medications and their formulations must also be documented.

6.3.3 Menstrual Baseline and Interval History

Baseline History

Age of menarche and cycle length and frequency will be obtained at the screening visit and reported in the CRF.

Interval History

The last menstrual period (date of first day of bleeding) will be collected at every visit and reported in the CRF.

6.3.4 Medication History

A medication history must be present, including start and stop dates. The table below lists the medications that must be included in the history and reported in the CRF.

Medication History Table

Medication Category	Complete History or Timeframe
Antiretroviral therapy	1 year prior to study entry
Immune-based therapy	1 year prior to study entry
Tuberculosis therapy	Complete
Hormonal contraceptive therapies including barrier methods	1 year prior to study entry
Blinded study treatment	30 days prior to study entry
Prescription drugs for treatment of opportunistic infections	30 days prior to study entry
Prescription drugs for prophylaxis of opportunistic infections	30 days prior to study entry
Prescription drugs (other)	30 days prior to study entry
Complementary and Alternative therapies	30 days prior to study entry
Dietary supplements	30 days prior to study entry
Other – In Vitro Fertilization (IVF)	30 days prior to study entry

6.3.5 Clinical Assessments

In addition to the visits specified in section 6.1, the clinical assessments (except height) should be performed when clinically indicated.

Complete Physical Exam

A complete physical examination will be conducted at screening and as part of clinical assessments performed when clinically indicated. The complete physical exam will include, at a minimum, an examination of the skin, head, mouth, and neck; auscultation of the chest; cardiac exam; abdominal exam; examination of the lower extremities for edema; and Karnofsky performance test. It will also include signs and symptoms, diagnoses, and vital signs (weight, height, temperature, pulse, respiration rate, and blood pressure).

Targeted Physical Exam

A targeted physical examination is required at all study visits after screening. The targeted physical exam must include vital signs (temperature, pulse, respiration rate, and blood pressure) and is to be driven by any previously identified or new signs or symptoms including diagnoses that the participant experienced.

Height

Height required to be reported on the CRF at study entry only.

Weight

Weight required at study entry and at all visits.

Waist Circumference

Waist circumference required at study entry and all on-study visits.

Signs and Symptoms

At entry, all grades that occurred 30 days before entry must be recorded in the source document and CRFs.

After entry:

- Grades 1 and 2 toxicities must be recorded in the source document.
- Grades 3 and 4 toxicities must be recorded in both the source document and CRF.
- Record all signs and symptoms that led to a change in treatment regardless of grade on both source document and CRF. Further evaluation will be required for those events that meet Expedited Adverse Event (EAE) or ICH reporting requirements.

Diagnoses

At the entry and post-entry visits, record all diagnoses identified by the ACTG criteria for clinical events and other diseases in the source document and CRFs.

HIV and TB Treatment Modifications

After entry, all modifications to antiretroviral medications and TB drugs including initial doses, subject-initiated, physician modifications and/or protocol-mandated interruptions, modifications, and permanent discontinuation will be recorded on the CRFs.

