1.3 Secondary Objectives

- 1.3.1. To estimate the area under the concentration-time curve (AUC), trough concentration (C_{\min}), maximum concentration (C_{\max}), apparent clearance (CL/F), and half-life ($t_{1/2}$) of MPA in HIV and TB coinfecting women taking EFV-based cART and RIF-containing TB treatment.
- 1.3.2. To estimate time and variability in time to MPA C_{\min} reaching 0.1ng/mL or less in HIV and TB coinfecting women taking EFV-based cART and RIF-containing TB treatment.
- 1.3.3. To estimate the proportion of participants who maintain MPA levels above the minimum level thought to suppress ovulation (MPA 0.1ng/mL) through 12 weeks after DMPA administration.
- 1.3.4. To evaluate the toxicity and safety of concurrent RIF, EFV, and DMPA use.

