4.1.5 Premenopausal female with presumed normal ovarian function based on normal menstrual history and absence of previous ovarian dysfunction diagnosis.

NOTE: Clinical assessment and clinician’s opinion are acceptable for determining previous ovarian dysfunction diagnosis.

4.1.6 Last menstrual period (LMP) ≤ 35 days prior to study entry.

4.1.6.1 If LMP is > 35 days prior to study entry, serum follicle-stimulating hormone (FSH) must be ≤ 40 MIU/mL.

NOTE: Enrollment after the start of the monthly menstrual flow is preferred.

4.1.7 Negative serum or urine-HCG pregnancy test within 30 days prior to study entry and negative pregnancy test at entry at any network-approved laboratory that operates in accordance with Good Clinical Practices and participates in appropriate external quality assurance programs.

4.1.8 All participants must agree not to participate in a conception process (eg, active attempt to become pregnant or in vitro fertilization) for the duration of the study.

Women of reproductive potential, who are participating in sexual activity that could lead to pregnancy, must agree to use an additional reliable method of contraception while in the study. Acceptable forms of contraceptives include:

- Condoms (male or female) with or without a spermicidal agent
- Diaphragm or cervical cap with spermicide
- Non-hormonal IUD
- Bilateral tubal ligation
- Male partner vasectomy

4.1.9 Laboratory values within 30 days prior to study entry:

- Absolute neutrophil count ≥ 500 cells/mm³
- Platelet count $\geq 50,000$ platelets/mm³
- Hemoglobin ≥ 8.0 g/dL
- Aspartate transaminase (AST) and alanine aminotransferase (ALT) < 5 x upper limit of normal (ULN)
- Creatinine ≤ 1.5 x ULN
- Total bilirubin ≤ 2.0 x ULN

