6.3.8 Laboratory Evaluations

At screening and entry all laboratory values must be recorded. For post-entry assessments, record all \geq Grade 3 laboratory values. All laboratory toxicities that led to a change in treatment, regardless of grade, must be recorded. Further evaluation will be required for those events that meet EAE or ICH reporting requirements. All protocol required labs will be done at the DAIDS-approved local lab unless otherwise specified.

Hematology

Perform hemoglobin, hematocrit, white blood cell count (WBC), absolute neutrophil count (ANC), and platelets as clinically indicated in addition to the visits specified in section 6.1.

Blood Chemistries

Perform electrolytes (sodium, potassium, chloride, and bicarbonate), creatinine, and blood urea nitrogen as clinically indicated in addition to the visits specified in section 6.1.

Liver Function Tests (LFTs)

Perform total bilirubin, AST (SGOT), and ALT (SGPT), albumin as clinically indicated in addition to the visits specified in section 6.1.

Pregnancy Test

At screening, serum or urine β -HCG (urine test must have a sensitivity of ≤ 25 mIU/mL) may be used.

Urine β -HCG may be used at the entry, post-entry, and premature study discontinuation visits and when clinically indicated.

There must be a negative pregnancy test within 30 days prior to study entry as well as at the time of study entry.

Perform as clinically indicated in addition to the visits specified in section 6.1.

Plasma Progesterone Levels

This will be done at a central lab. For details, please see the LPC found on the A5338 PSWP.

Serum FSH

At screening must be performed on women with LMP >35 days. For details, please see the current laboratory processing chart (LPC) found on the A5338 PSWP.

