9.2.2 Secondary Outcome Measures

9.2.2.1 Estimation of MPA PK parameters in HIV and TB co-infected women taking EFV and RIF:

MPA PK parameters AUC over the 12 weeks (AUC_{0-12wk}), C_{min} , C_{max} , apparent clearance (CL/F), and half-life ($t_{1/2}$) calculated using standard non-compartmental method: These PK parameters will be calculated based on the MPA concentrations obtained every 2 weeks over the 12 weeks. MPA concentration obtained at entry (prior to DMPA administration) will be evaluated as confirmation that no DMPA was taken prior to study entry.

9.2.2.2 Estimation of time and variability in time to reach MPA 0.1 ng/mL:

Times (weeks) where elimination slopes estimated fitting \log_e -linear regression models to the individual MPA concentrations obtained in the elimination phase reach MPA level of 0.1 ng/mL: The exact sampling time (weeks) will be used.

9.2.2.3 Estimation of the proportion of participants reaching MPA level <0.1 ng/mL at specified time points:

MPA concentration levels obtained at study weeks 6, 8, and 10. Since the week 12 measurements will be evaluated as the primary outcomes (section 9.2.1), the MPA measurements at study weeks 6, 8, and 10 after DMPA administration will be studied for any earlier sign of MPA levels <0.1 ng/mL.

9.2.2.4 Evaluation of toxicity and safety:

All adverse events with toxicity Grade ≥ 3 from signs/symptoms and chemistry and hematology laboratory analyses.

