9.6.2 Analyses of Secondary Outcome Measurements

9.6.2.1 Estimation of MPA PKs in presence of EFV and RIF:

MPA PK parameters AUC_{0-12wk} , concentration at week 12 (trough concentration, C_{min}), C_{max} , CL/F , and $T_{1/2}$ will be estimated using non-

compartmental approach and descriptive statistics of these PK parameters will be presented. For the purpose of evaluating whether these PK parameters are significantly different from those in women not on the companion drugs, those PK parameters will be compared to those from the historic controls (A5093 Control Arm) using nonparametric two-sample Wilcoxon test. GMRs in MPA PK parameters of co-administration over administration-alone and associated 90% CIs will also be presented to provide magnitude of the differences as a supplementary analysis.

9.6.2.2 Estimation of time and variability in time to reach a MPA 0.1 ng/mL:

Times (weeks) and variability in times to reach MPA 0.1 ng/mL will be estimated using the analysis methods described in section 9.6.1.

9.6.2.3 Estimation of the proportion of participants reaching MPA level <0.1 ng/mL:

The proportion and percentage of participants with MPA concentration levels <0.1 ng/mL will be summarized by each of the study weeks 8 and 10. 90% CI for proportion at each week will be presented using Clopper-Pearson exact method.

9.6.2.4 Evaluation of toxicity and safety:

Signs and symptoms, chemistry and hematology with toxicity Grade ≥ 3 will be tabulated by study week.

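### The Grade 3 or higher safety table does not separate findings present before the DMPA injection from those that begin or worsen after it, and it gives no count of women

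*Protocol*

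**What the plan says.** Secondary objective 1.3.4 is "To evaluate the toxicity and safety of concurrent RIF, EFV, and DMPA use". Outcome 9.2.2.4 serves it with "All adverse events with toxicity Grade" 3 or higher "from signs/symptoms and chemistry and hematology laboratory analyses". Analysis 9.6.2.4 takes "Signs and symptoms, chemistry and hematology with toxicity Grade" 3 or higher and says these "will be tabulated by study week". Neither section mentions baseline grade, onset or worsening, and neither asks for the number of women with an event.

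Pre-injection data are collected. For signs and symptoms, 6.3.5 says "At entry, all grades that occurred 30 days before entry must be recorded in the source document and CRFs". For laboratory tests, 6.3.8 says "At screening and entry all laboratory values must be recorded", although the schedule in 6.1 places hematology, chemistry and liver function tests at screening and weeks 4 and 12, with none at entry.

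After entry, 6.3.5 sends all Grade 3 and 4 signs and symptoms to the CRF, and 6.3.8 has all laboratory values of Grade 3 or higher recorded. Neither rule is limited to new findings.

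**The concern.** The study has one arm (9.3) and supplies one drug, DMPA (5.0). By the time of the injection each woman has been on RIF-containing TB treatment for at least 8 weeks and EFV-based cART for at least 4 weeks (2.2). Use of all three drugs together starts only at the injection, so the woman's own state just before it is the only internal reference for what the combination adds.

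The protocol's safety profiles show why this matters. Dizziness, insomnia and depression are listed for both DMPA (2.1.1) and EFV (2.1.3), and menstrual change for both DMPA (2.1.1) and RIF (2.1.2). A Grade 3 symptom at week 4 may be a continuing effect of earlier treatment or something that began after DMPA. The planned table shows the two alike. It is the only safety analysis the protocol specifies for this objective, so a reader of the results could not recover the distinction or learn how many women were affected.

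**Working it through.** This is mainly a check of text, because the plan states no safety figure to reproduce.

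**Path of one finding.** Take a Grade 3 sign or symptom present at entry that continues.

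1. Eligibility: 4.1.9 limits six types of laboratory value ("Laboratory values within 30 days prior to study entry": ANC, platelets, hemoglobin, AST/ALT, creatinine, bilirubin). Section 4.2 excludes recent serious illness and a Karnofsky score below 70. No criterion sets a general grade limit on symptoms or on electrolytes, so the woman can be enrolled.
2. Entry: the symptom goes on the CRF with its grade (6.3.5).
3. After entry: it goes on the CRF again, because all Grade 3 and 4 toxicities do (6.3.5). Symptoms are assessed at six post-entry visits (weeks 2, 4, 6, 8, 10 and 12). Laboratory tests are repeated at weeks 4 and 12.
4. Analysis: it enters the 9.6.2.4 table for each week in which it is recorded, with nothing to mark it as present before the injection.
5. SAP: it names objectives 1.3.1 and 1.3.2 only, so it adds no rule for 1.3.4.

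**Illustration of size.** Planned enrolment is n = 46 (9.4). The share p of women with a Grade 3 or higher finding that carries over from before the injection to a post-entry visit is not in the documents. It is assumed here to lie between 1% and 10%. Women are taken as independent. Expected number = 46p; chance of at least one = 1 − (1 − p)^46.

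| Assumed p | Expected women, 46p | Chance of at least one |
|---|---|---|
| 1% | 0.46 | 1 − 0.99^46 = 37% |
| 2% | 0.92 | 1 − 0.98^46 = 61% |
| 5% | 2.3 | 1 − 0.95^46 = 91% |
| 10% | 4.6 | 1 − 0.90^46 = 99% |

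No sample size or power figure in the protocol depends on this.

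**The case against.** The case for leaving the plan alone has several parts.

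- **The objective is the combination.** A reader might infer that pre-existing abnormalities will be reported as toxicity caused by DMPA. The documents do not support that. Objective 1.3.4 concerns the three drugs together, the table is descriptive, and nothing attributes its entries to DMPA. A RIF or EFV effect that continues during combined use is arguably within the objective. This stands, and it is a reason to keep such findings in the table. It is not a reason to leave them unmarked.
- **A by-week table is not a cumulative rate.** A reader might infer that an overall event rate is inflated by some factor, or that repeated recording is double counting. The plan produces no cumulative rate and does not add the weeks together. This stands; the gap is that the table lacks both a baseline reference and a count of women.
- **Carry-over may be rare.** Women must be stable on EFV (4.1.3). Section 2.1.3 says that CNS symptoms generally resolve after 2 to 4 weeks and most rash within a month. Section 2.1.2 puts significant RIF reactions below 4% of TB patients. This points to the lower part of the assumed range but does not settle the figure.
- **The entry limits may exclude Grade 3 laboratory values.** A reader might equally infer that the limits in 4.1.9 admit them. Neither can be shown, because the grading table is cited but not reproduced.
- **An adverse event may imply new onset, and 9.6 is only a summary.** Both readings are possible. The glossary only expands the abbreviation, however, and the SAP also omits the primary objectives, so its silence shows only that no rule has been written in the documents supplied.
- **A baseline rule can hide harm.** If the reference were the worst grade in the 30 days before entry, a symptom that had resolved and then recurred after the injection would be lost. This stands and shapes the fix.

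**Conclusion.** The concern holds as a limited one. Outcome 9.2.2.4 and analysis 9.6.2.4 make no use of the pre-injection grade and give no count of women, and the SAP adds nothing for 1.3.4. With no control arm and prior exposure to TB treatment and EFV in every woman, a Grade 3 or higher finding that predates the injection can appear indistinguishable from one that began under the three-drug combination.

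The size cannot be determined from the documents. Under the assumed 1% to 10% carry-over, it is about 0.5 to 4.6 of 46 women. In a table that may contain few events, even one or two such women could alter how it is read. The documents do not show that events would be attributed to DMPA or that any planned rate would be biased by a stated amount. The primary analysis is unaffected.

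**What to change.** In 9.2.2.4 and 9.6.2.4, or in a SAP section for objective 1.3.4:

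- Keep the by-week table of all Grade 3 or higher findings, so that no event is removed, and add a pre-injection column.
- Flag each post-injection finding as new or worsened, or as persisting unchanged.
- Report the number of women with at least one new or worsened Grade 3 or higher finding through week 12, with an exact 90% CI (the Clopper-Pearson method already used in 9.6), alongside the number with any Grade 3 or higher finding.
- Define baseline as the grade present at the injection. For symptoms this is the status at entry, so a symptom that resolved before entry and recurs counts as new. For hematology, chemistry and liver tests it is the last value before the injection, which is the screening value because none is scheduled at entry.
- State that liver function tests are included. They have their own row in the schedule, while 9.2.2.4 and 9.6.2.4 name only chemistry and hematology.

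The cost is a few sentences and a little programming, with no new visits or samples. The protocol does not say whether the entry form separates resolved from ongoing symptoms; if it does not, entry status must be taken from source documents. Two limits remain. The laboratory baseline may be up to 30 days old. Post-entry Grade 1 and 2 symptoms generally stay in source documents, so the CRF will not always show whether a persisting symptom eased in between.
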